### Secondary Objective:

- 1. To estimate and compare the IR of endometrial cancer among women aged  $\geq$ 50 years with a uterus and without prior hormone therapy use, in the following groups:
  - a. LDVE new users versus E+P HT new users of hormone therapy.
  - b. MDVE new users versus E+P HT new users of hormone therapy.
  - c. HDVC new users versus E+P HT new users of hormone therapy (HIRD only).

### 9. RESEARCH METHODS

## 9.1. Study Design

This is a non-interventional, retrospective cohort study among women aged  $\geq$ 50 years using a US healthcare claims data source (the HIRD) and longitudinal data collected from five Swedish National Registers. The three exposed groups are new users of vaginal estrogen grouped into 3 dose categories: LDVE, MDVE, and HDVC (HIRD only) regardless of prior use of hormone therapy (full study population). The comparator groups are non-users with no prior vaginal estrogen use, regardless of other prior use of hormone therapy and E+P HT new users with no prior use of hormone therapy. Incidence rates of endometrial cancer will be presented and adjusted hazard ratios will be estimated for each exposure group as compared to both non-users of vaginal estrogen and E+P HT new users.

### 9.1.1. Time Periods

The study period, i.e., the beginning of the baseline period to the end of the follow-up period, is 01 January 2006 (earliest available date) through 31 December 2020 (or most recent available date) in the HIRD, and 01 January 1997 (earliest available date for medical record history) through 31 December 2019 (or most recent available date) in the Swedish registers. The difference between the two data sources in end of study dates is due to the difference in the lag time for populating the HIRD and the Swedish registers.

Ascertainment of exposure and follow-up will be 01 January 2007 - 31 December 2020 (or most recent available date) in the HIRD, and 01 July 2007 - 31 December 2019 (or most recent available date) in the Swedish Registers to allow for a 12- or 24-month baseline period in the HIRD and Swedish data bases, respectively. The index date is the day of initiating a study drug or, for non-users, the date of a gynecological visit that meets all inclusion and exclusion criteria. For new users of vaginal estrogens and E+P HT, a 6-month induction period is allowed following initiation of exposure and prior to beginning follow-up to allow for induction and diagnosis of endometrial cancer (Figure 1). For non-users, follow-up and accrual of person-time starts the day after the index date. The unexposed period before a woman starts any vaginal estrogen will be included as time at risk for a non-user until they begin using one of these drugs. The unexposed time at risk (non-users) will be censored if and when they start using vaginal estrogen, E+PHT or other non-study estrogen or progestogen medications. A sensitivity analysis is included that varies the length of the induction period and includes an induction period for the non-user cohort. Table 1 summarizes the different time periods for the two data sources. Patients may differ in their follow-up dates depending on when they meet the study inclusion, exclusion, and censoring criteria.

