#### 9.2.2. Exclusion Criteria

Patients meeting any of the following criteria will not be included in the study:

Exclusion criteria are applied to all treatment and comparator groups unless otherwise noted. Information during the baseline period is used to assess whether a subject meets the criteria unless otherwise noted (see definitions in Section 9.3 Variables). The exclusion criteria will include the following (summarized in Figure 3 above):

- Hysterectomy;
- Endometrial cancer;
- ≥1 prior dispensing of any vaginal estrogen (including study drugs and non-study drugs) prior to the index date for new users of vaginal estrogen. For non-users and E+P HT new users, this criterion will be assessed during the entire baseline period, including the potential index dates.
- $\geq 2$  dispensings of vaginal estrogen drugs on the index date that differ by strength, formulation, or active ingredient.
- Secondary analyses only:
  - $\circ \geq 1$  prior dispensing of E+P HT prior to the index date for new users of E+P HT. For vaginal estrogen users, this criterion will be assessed during the entire baseline period, including the index date;
  - $\circ \geq 1$  prior dispensing of vaginal or non-vaginal progestogen hormone therapy product (single-entity or combination, except contraceptives) not included as E+P HT study drugs.
  - ≥1 dispensing of oral, transdermal, or injectable estrogen hormone therapy product (single-entity or combination, except contraceptives) not included as E+P HT study drugs.

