### 9.4.2. Swedish Registers, Sweden

The Swedish registry data include five large, nationally held registers: the Swedish NPR, the Swedish Prescribed Drug Register (SPDR), the Swedish Cancer Register (SCR), the Cause of Death Registry, and the Total Population Register (TPR). These registers include data for patients, drugs, cancer, death, and the population linkable by patients' personal identity numbers. Entrance into the registers is upon birth or immigration to Sweden and exit from the registers is upon death or emigration.

Healthcare in Sweden is primarily government-funded and managed at the national, regional, and local level. Only a small proportion of the population (6%) also have some type of supplementary private health insurance. In most regions, there is no formal gatekeeping and patients may contact specialists directly. Applications for data access are sent to the National Board of Health and Welfare and Statistics Sweden and processed by a pre-defined data permit process. The data permit process is preceded by a separate ethical review process by the Swedish Ethical Review Agency. The five Swedish registers are detailed below.

- The Swedish NPR includes information regarding inpatient and outpatient non-primary (i.e., specialist) encounters across Sweden; outpatient general practice encounters are not captured in the NPR. Beginning in 1987, coverage for inpatient admissions became nationwide and is near 100%. Coverage for outpatient non-primary care began nationwide in 2001 and is around 87% (although it may be higher for somatic care such as rheumatology). Key variables include diagnosis, surgery, external causes of injury (E codes), age, sex, hometown, hospital, specialty, and information related to hospital admissions and discharges (e.g., dates, main and contributory diagnoses, mode of discharge). Information on patient anthropometric data (e.g., height, weight, body mass index [BMI]) is not available nor are laboratory test results (e.g., absolute lymphocyte count, blood lipid levels) or clinical measurements (e.g., blood pressure). A number of diagnoses have been reported to have high positive predictive values in the inpatient register. The NPR is updated annually.

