- The SPDR, maintained by the National Board of Health and Welfare, contains information on all prescribed and dispensed medication for patients in Sweden. The SPDR was started in July 2005. The register contains data recorded using personal identification numbers and can thus be linked with other Swedish registers. Coverage of prescriptions is close to 100%, however, inpatient administrations and hospital administered drugs in specialized outpatient care are not captured. Information recorded in the SPDR includes basic demographic characteristics such as age, sex, and residency, as well as medication-specific information such as the prescribed/dispensed drug (e.g., ATC code, International Non-proprietary Names), prescription dispensing date, pack size, dispensed amount, formulation, dosage, prescribing healthcare practitioner, and costs. The SPDR is updated monthly.
- The Swedish Cancer Register was started in 1958 and is managed by the National Board of Health and Welfare. The registry records every cancer case diagnosed by clinical, morphological or other laboratory examinations as well as cases diagnosed at autopsy. Since the mid-1980s there are six regional registries associated with the oncological centers in each medical region of Sweden where the registration, coding and major check-up and

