- 9. HIRD and Sweden: A quantitative bias analysis will be conducted to evaluate the impact of potential under-ascertainment of hysterectomy and misclassification of prior use of systemic estrogens or other estrogen- or progestogen-containing products on effect estimates of endometrial cancer rate with LDVE use (Annex 1: Table 11 and Table 12). There may be women whose hysterectomy, prior estrogen use (including prior E+P HT use), or prior progestogen use is not captured in the data sources in each country prior to the index date, in which case, they would not have been excluded at baseline. This analysis will use plausible

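### Sweden: the 1997 look-back floor is called the earliest available, but the protocol's own register descriptions reach back to 1987 and 1958, so some earlier hysterectomies and endometrial cancers can be missed

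*Protocol*

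**What the plan says.** Protocol section 9.1.1 defines the period at issue: "The study period, i.e., the beginning of the baseline period to the end of the follow-up period". For Sweden this is "01 January 1997 (earliest available date for medical record history) through 31 December 2019 (or most recent available date) in the Swedish registers", and Table 1 repeats it. The 1997 date is therefore the floor of the Swedish baseline. Exposure ascertainment and follow-up run over "01 July 2007 - 31 December 2019 (or most recent available date) in the Swedish Registers".

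Section 9.4.2 describes the same registers differently. On the National Patient Register: "Beginning in 1987, coverage for inpatient admissions became nationwide and is near 100" per cent. It lists surgery and diagnosis among that register's key variables. On cancer: "The Swedish Cancer Register was started in 1958 and is managed by the National Board of Health and Welfare".

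Section 9.2.2 lists hysterectomy and endometrial cancer as exclusions and adds: "Information during the baseline period is used to assess whether a subject meets the criteria unless otherwise noted". Section 9.2.1 says that the baseline takes in all the medical history available up to the index date, with a Swedish minimum of 24 months.

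Section 9.7.4, item 9, accepts that exclusion can fail: "There may be women whose hysterectomy, prior estrogen use (including prior E+P HT use), or prior progestogen use is not captured". It plans a quantitative bias analysis in both countries.

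**The concern.** Every objective is restricted to women with a uterus. Hysterectomy is permanent, so an operation at any earlier date matters, and a woman who has had one adds person-time but cannot have the event. A look-back shorter than the registers allow leaves more such women in the cohorts than necessary. It can likewise admit women with endometrial cancer before 1997 as if they were free of the disease.

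The incidence rates are study results in their own right, and missed hysterectomy lowers them. The hazard ratios are at risk if under-capture differs between groups. That is possible because the groups enter by different routes: vaginal estrogen users on a dispensing, non-users on a gynecological visit, E+P HT users on a dispensing of a combined product. Any Swedish bias would carry into the pooled estimates of section 9.7.5.

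**Working it through.** **1. The statements side by side.** Section 9.1.1 and Table 1 make 1997 the earliest available history. Section 9.4.2 gives nationwide inpatient data ten years earlier and cancer registration 39 years earlier (1997 - 1958). Section 9.2.1 promises all available history. These do not fit together unless 1997 reflects a limit that the protocol does not state.

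**2. Length of look-back.** Years from each start date (taken as 1 January) to the first and last possible Swedish index dates:

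| Start | To 01 July 2007 | To 31 December 2019 |
|---|---|---|
| 1997 (plan) | 10.5 | 23.0 |
| 1987 (inpatient) | 20.5 | 33.0 |
| 1958 (cancer register) | 49.5 | 62.0 |

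For a woman aged 65 at index, the record begins at this age:
- Index July 2007: 65 - 10.5 = 54.5 under the plan; 65 - 20.5 = 44.5 from 1987.
- Index end of 2019: 65 - 23 = 42 under the plan; 65 - 33 = 32 from 1987.

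If index dates were spread evenly (an assumption), the midpoint is 6.25 years after July 2007. Look-back under the plan is then 10.5 + 6.25 = 16.75 years.

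**3. The plan's size figures, for context.** Events = (1.960 + 0.842)² / (0.2 × 0.8 × (ln 1.5)²) = 298.4, rounded up to the stated 299. Person-years = 298.4 / 0.000704 = about 423,846. One fifth is 84,769 (stated 84,770), and dividing by 2.4 years gives 35,320 exposed women (stated 35,321). The figures reproduce. With 100,800 exposed women at 1:4, expected events are 100,800 × 5 × 2.4 × 0.000704 = 851.6, and power is 99.7%.

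**4. What missed hysterectomy would do.** Let u be the share of person-time from women with an undetected hysterectomy. The protocol gives no value, so the following is illustrative only.
- Observed rate = true rate × (1 - u). From 70.4 per 100,000 person-years, u = 2% gives 69.0 and u = 20% gives 56.3.
- HR factor = (1 - u in exposed) / (1 - u in comparator). If u is equal, the factor is 1, and power at u = 20% is still 98.8%.
- If u is 15% in the exposed and 2% in the comparator: 0.85 / 0.98 = 0.87. Reversed: 0.98 / 0.85 = 1.15. A true HR of 1.5 would appear as 1.30 or 1.73.
- A smaller gap, 15% against 10%: 0.85 / 0.90 = 0.94.

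Here u covers all undetected hysterectomy, including operations before 1987 that neither start date captures. It does not measure the effect of choosing 1997.

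**5. What the planned bias analysis covers.** Item 9 is framed around LDVE, and the title of Table 11 in Annex 1 names LDVE users against non-users. Its inputs are assumed values. It covers hysterectomy and prior hormone use, but not prior endometrial cancer, MDVE or the E+P HT comparisons.

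**The case against.** **Already disclosed.** Item 9 states the mechanism for hysterectomy and plans to quantify it. This stands, and it makes the point an improvement rather than an unrecognised flaw. It does not explain why the loss is modelled from assumed inputs where section 9.4.2 indicates that data exist.

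**A coding reason is possible.** Section 9.3 names ICD-10-SE for patient-register diagnoses, named Swedish and Nordic classifications for procedures, and ICD-O-2/3 for tumours. The start of coverage is not the same as usability under those codes, and access depends on ethical review and a data permit. This also stands. But the protocol does not link 1997 to coding or permits; it calls the date the earliest available.

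**Matching may help.** Age, calendar year of index and length of baseline are candidate propensity-score covariates. Balancing them would align the opportunity to detect an earlier operation. It would not ensure equal prevalence of operations before 1997.

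**Stronger readings that the documents do not support.** A reader might infer that every woman operated on before 1997 is counted as having a uterus. She is misclassified only if no record from 1997 onward reveals the operation. A reader might take 10.5 years as the look-back for the whole cohort; it applies only to the first index date. A reader might conclude that the 1997 date makes the Swedish rates 10-20% too low or pulls the hazard ratio down. No prevalence is given, the direction of any difference between groups is not established, and a 1987 start would recover only part of what is missed.

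**Conclusion.** The inconsistency is real: the stated earliest date does not agree with the protocol's own account of the registers, and no reason for it is given. The plan as written can retain some Swedish women without a uterus or with earlier endometrial cancer who might be identified from register data that the protocol describes.

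The size is unknown. Missed hysterectomy lowers the Swedish incidence rates; the hazard ratios are affected only if under-capture differs between groups. Power is not threatened under the illustrative values above. For endometrial cancer before 1997, the documents support neither a number nor a direction. This is a low-cost improvement to exclusion accuracy, not evidence that the Swedish result is invalid.

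**What to change.** In section 9.1.1, Table 1 and section 9.2.2, set a separate Swedish look-back for the two lifetime exclusions:

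- Hysterectomy: inpatient patient-register data from 1987.
- Endometrial cancer: the cancer register from its start.
- Add the older code versions to Appendix G. The 1997 start can remain for other covariates.
- Report how many women the 1987-1996 inpatient data exclude in each group, and use that yield to inform the hysterectomy inputs of sensitivity analysis 9.

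The cost is a wider date range in the Swedish data application and the mapping of older codes. Somewhat fewer women will qualify.

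If 1997 is a real coding or permit limit, replace the claim that it is the earliest available date with that reason. Then extend sensitivity analysis 9 to missed prior endometrial cancer and to the MDVE and E+P HT comparisons.

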### Figure 1. Study Time Periods Between Treatment and Comparator Groups

### A. New user of vaginal estrogen or E+P HT

#### **B. Non-users**

Baseline period	Follow-up	Censored
Date of qualifying gynecologist visit		_

Abbreviations: E+P HT, estrogen-progestogen combination hormone therapy.

### Table 1. Study Time Periods Between the HIRD and Swedish National Registers

Time Period	HIRD	Swedish National Registers
Study period	01 January 2006 (earliest available date) – 31 December 2020 (or most recently available date)	01 Jan 1997 (earliest available date for medical record history) – 31 December 2019 (or most recently available date)
Baseline period	At least 12 months prior to and including index date	At least 24 months prior to and including index date
Exposure a scertainment period	01 January 2007 – 31 December 2020	01 July 2007 – 31 December 2019
Induction period (vaginal estrogen and E+PHT users)	(Index date + 1 day) + 6 months	(Index date + 1 day) + 6 months
Follow-up period (vaginal estrogen and E+PHT users)	Last day of induction period + 1 day – censored date	Last day of induction period + 1 day – censored date
Follow-up period (non-users)	Index date + 1 day – censored date	Index date + 1 day – censored date

**Abbreviations**: E+P HT, estrogen-progestogen combination hormone therapy; HIRD, HealthCore Integrated Research Database.SM

### 9.1.2. Exposure and Comparator Groups

The study will include three vaginal estrogen new user exposure groups: LDVE, MDVE, and HDVC (HIRD only). The two comparator groups are non-users of vaginal estrogens regardless of prior use of hormone therapy and new users of E+P HT without any prior hormone therapy use.

#### PFIZER CONFIDENTIAL

[figure not shown]
CT24-WI-GL02-RF023.0 Non-Interventional Study Protocol Template For Secondary Data Collection Study 20-May-2021

Page 20

The study population and characterization of the exposure and comparator groups are illustrated as a flowchart in Figure 2.

Due to the higher estrogen concentration for Premarin VC than non-Premarin LDVEs, higher daily doses of Premarin VC of >0.45 mg/day conjugated estrogen will be analyzed as a separate exposure group (HIRD only, as Premarin VC is not marketed in Sweden). This exposure group is referred to throughout as the HDVC group. Low-dose regimens  $\leq 0.3$  mg/day conjugated estrogen are also indicated for Premarin VC (i.e., 0.5 grams applied daily for 21 days or 0.5 grams applied twice weekly). These low-dose regimens will be evaluated as part of the LDVE exposure group.

### **Figure 2: Study Population**

Abbreviations: E+P HT, estrogen-progestogen combination hormone therapy; HDVC, high-dose Premarin VC (HIRD only); HIRD, HealthCore Integrated Research Database; LDVE, low-dose vaginal estrogen; MDVE, moderate-dose vaginal estrogen.

Note: Bolded boxes outlined in blue indicate an exposure or comparator group.

The three vaginal estrogen exposure groups and the two comparator groups are described below and summarized in Figure 2 (for definitions of study drugs and gynecological visits, see Section 9.2 Setting and Section 9.3 Variables):

- Exposure 1: New Users of LDVE.
  - o Women who had ≥1 dispensing of an LDVE during the exposure ascertainment period with prescription daily doses ≤10 mcg estradiol or ≤0.3 mg conjugated estrogen at cohort entry and no prior dispensings of vaginal estrogen. Low-dose Premarin VC (HIRD only) is defined as 0.5 g/day dose (equal to daily average strength 0.3 mg or less conjugated estrogens. It should be noted that these women may or may not have used hormone therapy prior to the index date and will be included regardless of such prior use.
- Exposure 2: New Users of MDVE.
  - Women who had ≥1 dispensing of a MDVE during the exposure ascertainment period with prescription daily doses >10 mcg 25 mcg estradiol or >0.3 mg 0.45 mg conjugated estrogen at cohort entry and no prior dispensings of vaginal estrogen. It should be noted that these women may or may not have used hormone therapy prior to the index date and will be included regardless of such prior use. The Swedish cohort will only include subjects with ≥ 1 dispensing of 25mcg estradiol (Vagifem).
- Exposure 3: New Users of HDVC (HIRD Only).
  - Women who had ≥1 dispensing of Premarin VC during the exposure ascertainment period with prescription daily doses >0.45 mg conjugated estrogen at cohort entry and no prior dispensings of vaginal estrogen. It should be noted that these women may or may not have used hormone therapy prior to the index date and will be included regardless of such prior use.
- Primary Comparator: Non-users of vaginal estrogen.
  - Women who had  $\geq 1$  gynecological visit during the exposure ascertainment period, and no dispensings of vaginal estrogen prior to or on the gynecological visit. It should be noted that these women may or may not have used hormone therapy prior to the index date and will be included regardless of such prior use.
  - The unexposed period before a woman starts any vaginal estrogen will be included as time at risk for a non-user until they begin using one of these drugs. The unexposed time at risk (non-users) will be censored when they start using vaginal estrogen, E+P HT or other non-study progestin or estrogen medications.
- Secondary Comparator: New Users of E+P HT.
  - Women who had  $\geq 1$  dispensing of E+P HT during the exposure ascertainment period, and no prior dispensings of any hormone therapy (excluding contraceptives).

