#### PFIZER CONFIDENTIAL

01 July 2007 to 31 December 2019 (or most recent available date) in the Swedish National Registers (the exposure ascertainment period). Similarly, two additional exposure groups will be created for MDVE (daily doses >10 mcg – 25 mcg/day estradiol or >0.3 mg – 0.45 mg/day conjugated estrogen) and, in the HIRD only, HDVC (daily doses >0.45 mg/day conjugated estrogen). These two additional groups will also include women with  $\geq$ 1 dispensing of MDVE or HDVC, respectively, regardless of prior use of hormone therapy. The difference in study periods between the HIRD and Swedish databases is due to the difference in lag time for data availability between the two data sources. The comparator groups are: (1) women with  $\geq$ 1 gynecological visit (i.e., non-users) and (2) new users of E+P HT with no prior use of hormone therapy. Women with less than 12 months of continuous health plan enrollment in the HIRD or less than 24 months of medical history in Sweden prior to the index date, without a uterus, or with a history of endometrial cancer will be excluded.

**Variables:** Vaginal estrogen use will be determined using prescription drug codes from pharmacy claims and dispensings. Diagnosis of endometrial cancer will be identified in the HIRD using codes that have been validated in the HIRD, and in Sweden using records in the Swedish Cancer Register. Covariates will include patient demographics, comorbidities, medications, and healthcare utilization. A listing of study variables is provided in Section 9.3 Variables.

**Data Sources:** The HIRD is a longitudinally integrated research database comprising automated payment claims for healthcare encounters since 01 January 2006 from included health insurance plans across the US. It is among the largest of its kind in the US, with current enrollment of approximately 70 million members as of 2018. The HIRD has been extensively used for pharmacoepidemiologic research, including many post approval safety studies. The HIRD includes enrollment data, medical care, physician specialty, laboratory results (one third of patients), prescription drug use, and healthcare utilization that can be tracked for each individual throughout the course of their enrollment.

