The United States (US) Food and Drug Administration (FDA) has issued a post-marketing requirement (PMR) to each Marketing Authorizations Holder (MAH) of an LDVE for an observational study to evaluate the rate of endometrial cancer among postmenopausal women with a uterus who use LDVE unopposed by a progestogen. Pfizer is the MAH for Estring® 2 mg (vaginal ring, 7.5 mcg/24 hours) and Premarin® Vaginal Cream 0.625 mg/gram (Premarin VC) and received a PMR notification for each product. Premarin VC has a higher estrogen concentration but is indicated for both low-dose and high-dose treatment regimens. In order to address the safety concerns for Premarin VC set forth in the PMRs, Pfizer includes Premarin VC in this study, with high-dose regimens evaluated as a separate exposure group. Analyses including Premarin VC will only be conducted in the HealthCore Integrated Research DatabaseSM (HIRD) as Premarin VC is not marketed in Sweden. A comprehensive feasibility assessment (submitted to the FDA on 28 June 2018) was conducted to ensure a scientifically valid observational study could be successfully executed using the HealthCore Integrated Research DatabaseSM (HIRD). This protocol describes the non-interventional study that will be conducted in the US and Sweden to fulfill the PMR commitment to the FDA to assess endometrial cancer risk among users of LDVE. Sweden was specifically requested by the FDA in order to fulfill this PMR. This non-interventional study is designated as a Post-Authorization Safety Study (PASS) and is a post-marketing commitment to the FDA.

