### 9.3.1. Exposures, Comparators, and Treatment Episodes

GPI codes will be used to identify vaginal estrogen and E+P HT products in the HIRD, (Annex 1: Appendix B) and ATC codes, formulation, brand name, and strength will be used to identify vaginal estrogen and E+P HT Swedish products (Annex 1: Appendix F). Gynecological visits for non-users will be identified in the HIRD using ICD-9-CM and ICD-10-CM diagnostic codes, HCPCS codes for annual exams, CPT codes for pap smear procedures, and physician's specialty code (Annex 1: Appendix C). Gynecological visits will be captured as non-primary outpatient care in the Swedish NPR. Proxies for gynecological visits (i.e., related procedure codes, specialist encounters, and/or reimbursement) will be considered, as appropriate.

Treatment episodes (Annex 1: Appendix I) will be created based on segments of continuous use among the study drug treatment groups, i.e., LDVE, MDVE, HDVC, and E+P HT. Continuous use is defined as consecutive drug dispensings for a treatment group, with no more than 90 days between the end of the days' supply of the earlier prescription and the dispensing date of the next prescription. In order to determine exposure status for vaginal estrogen users during the treatment episode, daily dose must first be computed for each prescription starting with the index dispensing. In the HIRD, daily dose for vaginal estrogen dispensings will be calculated as the drug strength dispensed multiplied by the drug quantity and divided by the days' supply. In Sweden, days' supply is not directly available from the SPDR. Thus, days' supply and daily dose will be estimated for each dispensed vaginal estrogen prescription based on assumptions such as defined daily dose and duration for use. For the E+P HT comparator group, dispensed amount of drug, drug strength and defined daily dose will be used to construct treatment episodes of continuous use. Exposure definitions will be further detailed in the statistical analysis plan (SAP).

The prescription daily doses of the vaginal estrogen dispensings will then be categorized as follows:

- LDVE: <10 mcg/day estradiol or <0.3 mg/day conjugated estrogen;
- MDVE: >10 25 mcg/day estradiol or >0.3 0.45 mg/day conjugated estrogen;
- HDVC: >0.45 mg/day conjugated estrogen.

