Vaginal estrogen users will enter the exposure group corresponding to the dose of their first study drug dispensing. Women whose first dispensing was E+P HT will enter the E+P HT comparator group. If a vaginal estrogen user changes dose categories or switches to E+P HT, she will be censored on the dispensing date of the new prescription. Similarly, if an E+P HT user switches to vaginal estrogen use, she will be censored on the vaginal estrogen dispensing date.

Patients may use different products and strengths for study drugs within their treatment group. If there are overlapping prescriptions for different products within the same treatment group, then it will be assumed that the patient stopped taking the first prescription drug and started the second prescription drug on the day it was dispensed (no stockpiling). If the patient has overlapping prescriptions for the same drug and dose, the prescriptions will be stockpiled, i.e., the overlapping days from the second prescription will be added to the end of the days' supply of the first

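### Premarin VC at 0.5 g per supplied day is defined as low dose, but at 0.625 mg/g it computes to 0.3125 mg/day, which the HIRD dose rule places in MDVE

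*Protocol*

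**What the plan says.** Section 7 gives the product as "Vaginal Cream 0.625 mg/gram (Premarin VC"). Section 9.1.2 names two low-dose regimens, "0.5 grams applied daily for 21 days or 0.5 grams applied twice weekly", describes them as at most 0.3 mg/day, and adds: "These low-dose regimens will be evaluated as part of the LDVE exposure group". The definition of the first exposure group in the same section repeats the point: "Low-dose Premarin VC (HIRD only) is defined as 0.5 g/day dose (equal to daily average strength 0.3 mg or less conjugated estrogens".

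The next band up, MDVE, is given in the Section 4 abstract as ">0.3 mg – 0.45 mg/day conjugated estrogen", with the same limits in Sections 9.1.2 and 9.3.1. High-dose Premarin VC (HDVC) lies above 0.45 mg/day.

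Section 9.3.1 makes these bands operational. In the HIRD, daily dose is "the drug strength dispensed multiplied by the drug quantity and divided by" the days' supply, and the result is then categorised. On group entry it states: "Vaginal estrogen users will enter the exposure group corresponding to the dose of their first study drug dispensing". Sections 9.2.3 and 9.3.1 censor a woman when a later dispensing falls in another dose category. Section 9.3.1 also notes: "Exposure definitions will be further detailed in the statistical analysis plan (SAP").

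**The concern.** The dose that defines low-dose Premarin VC does not meet the cut-off with which it is equated. A programmer who follows Section 9.3.1 and one who follows the product definition in Section 9.1.2 would put the same HIRD record in different exposure groups.

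The group decides which primary comparison a woman enters: LDVE versus non-users (1a) or MDVE versus non-users (1b). The same cut-off feeds the secondary comparisons with E+P HT, the HDVC-versus-LDVE sensitivity analysis and the HIRD estimates that are pooled with Sweden. It also drives censoring. A woman whose record moves from 0.5 g daily to 0.5 g twice weekly stays within low dose according to Section 9.1.2. Under the computed dose she passes from MDVE to LDVE and is censored. If that happens in the six-month induction period, Section 9.2.3 gives her no follow-up in the main analysis.

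**Working it through.** **Inputs.** Strength 0.625 mg/g (Section 7). Low-dose definition 0.5 g/day, and regimens of 0.5 g daily for 21 days or twice weekly (Section 9.1.2). LDVE up to 0.3 mg/day, MDVE above 0.3 to 0.45 mg/day, HDVC above 0.45 mg/day (Sections 4 and 9.1.2). Section 9.3.1 prints the LDVE limit with a strict inequality; this makes no difference below.

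**Formula (Section 9.3.1, HIRD).** Daily dose = strength × quantity / days' supply.

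**The plan's own equivalence.** 0.5 g/day × 0.625 mg/g = 0.3125 mg/day. The stated 0.3 mg or less is not reproduced. The excess is 0.3125 − 0.3 = 0.0125 mg/day, and 0.0125/0.3 = 4.2%. The figure becomes 0.3 only when rounded to one decimal, a step the available text does not state; the MDVE upper limit is given to two decimals.

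**The cut-offs in grams of cream.**
- LDVE ceiling: 0.3/0.625 = 0.48 g/day.
- MDVE ceiling: 0.45/0.625 = 0.72 g/day.

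The records that conflict with the stated intent are therefore those above 0.48 and up to 0.50 g/day. Expressed without any fill size, LDVE needs at least 0.625/0.3 = 2.083 days' supply per gram, whereas 0.5 g/day gives exactly 2.000.

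**The named regimens.** The protocol gives no fill size. For the 21-day regimen, assume a fill for 21 doses: 21 × 0.5 = 10.5 g, or 10.5 × 0.625 = 6.5625 mg.

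| Record | Daily dose (mg) | Group by rule | Group by Section 9.1.2 |
|---|---|---|---|
| 0.5 g on every supplied day | 0.3125 | MDVE | LDVE |
| 21-day regimen, days' supply 21 | 6.5625/21 = 0.3125 | MDVE | LDVE |
| 21-day regimen, days' supply 22 | 6.5625/22 = 0.298 | LDVE | LDVE |
| 21-day regimen, days' supply 28 | 6.5625/28 = 0.234 | LDVE | LDVE |
| 0.5 g twice weekly | 2 × 0.3125/7 = 0.089 | LDVE | LDVE |

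The conflict arises only where days' supply counts application days alone.

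**With an LDVE limit of 0.3125 mg/day.** The ceiling becomes 0.3125/0.625 = 0.50 g/day, all five rows fall in LDVE, and the HDVC boundary does not move.

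**The case against.** The best defence has four parts.

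- **The protocol speaks of a daily average.** Averaged over a cycle, both named regimens can be below 0.3 mg/day. This stands for twice-weekly use, and for the 21-day regimen if days' supply includes the week off. It does not rescue 0.5 g on every supplied day, because Section 9.1.2 states the definition per day and Section 9.3.1 divides by recorded days' supply, not by cycle length.
- **The product-specific sentence should override the general band, with 0.3 as a rounded 0.3125.** The intent is indeed clear, and rounding is a plausible origin. But the available text states neither rounding nor precedence. That absence cannot be put more strongly: a superscript marker in the LDVE definition has no visible note, and Annex 1 Appendices A and I are stand-alone documents not at hand.
- **The SAP will add exposure detail.** It may, and it was not available here. Still, both conflicting values are already fixed in the protocol, so this is a contradiction and not a detail left for later.
- **The bands are referenced to dose-conversion guides, and moving one may depart from them.** Those guides could not be checked. However, Premarin VC is the only conjugated-estrogen product in the Section 9.2.1 list of vaginal study drugs, so a product rule and an amended conjugated-estrogen band have the same effect here.

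A reader might infer that low-dose Premarin VC users generally land in MDVE, or that the primary hazard ratios are biased. The protocol supports neither: it does not say how days' supply is recorded or how many records lie between 0.48 and 0.50 g/day. Nor should apparent dose switches in general be blamed on this error, since any cut-off on a dose computed from days' supply produces some.

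**Conclusion.** The point holds as an internal contradiction. At the stated strength, 0.5 g per supplied day is 0.3125 mg/day, 4.2% over the LDVE ceiling, and the HIRD rule as written sends that record to MDVE against the stated assignment. This follows from the protocol's own figures. The reach is narrow: Premarin VC in the HIRD only, records above 0.48 and up to 0.50 g/day, and only where days' supply counts application days. The other HIRD products, the HDVC boundary and the Swedish cohort definitions are unaffected. The 28-day result rests on the assumed 10.5 g fill. The number of women and the size or direction of any change in the hazard ratio are unknown. It should be fixed, because the affected dose is the one the protocol itself names as low dose for a product under the post-marketing requirement, and group entry and censoring both depend on it.

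**What to change.** Before cohort construction, in Sections 4, 9.1.2 and 9.3.1:

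- State that Premarin VC at 0.5 g/day or less (0.3125 mg/day or less of conjugated estrogen) is LDVE.
- State MDVE for conjugated estrogen as above 0.3125 to 0.45 mg/day, and leave HDVC at above 0.45 mg/day.
- Replace the equivalence of 0.5 g/day with 0.3 mg or less by 0.3125 mg.
- Test the classification code on three records: 0.5 g daily, the 21-day regimen and twice weekly. All should return LDVE.

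No tolerance above 0.5 g/day is needed to remove the contradiction, and the protocol offers no basis for one. The change will not remove every apparent dose switch caused by variation in days'-supply entry. The cost is the wording of one cut-off and one programming check, with no additional data.
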